5.1.1 Study design for subjects with moderate to severe chronic plaque PSO

5.1.1.1 Period 1: Screening

The Screening Period of 2 to 5 weeks will be used to confirm eligibility; obtain laboratory data; verify that the doses of nonsteroidal anti-inflammatory drugs (NSAIDs) and other pain relievers, such as acetaminophen, paracetamol, or mild opiates, if used to treat PsA are stable; and enable washout of any medications not permitted for use during the study.

5.1.1.2 Period 2: Week 0 to Week 16

Eligible subjects will be allocated to the following study treatments in a 2:2:1 ratio:

- CZP 400mg (n=50): CZP administered sc at the dose of CZP 400mg Q2W
- CZP 200mg (n=50): CZP administered sc at the dose of CZP 400mg at Weeks 0, 2, and 4, followed by CZP 200mg Q2W (starting at Week 6)
- PBO (n=25): PBO administered sc Q2W

Study treatments (including PBO) will be administered by dedicated, unblinded, trained site personnel at Baseline and Q2W thereafter to Week 16.

5.1.1.3 Period 3: Week 16 to Week 52

The treatment received in Period 3 will be based on response to double-blind treatment at Week 16. All CZP and PBO treatments will be administered by dedicated unblinded site personnel at site visits, excluding the escape treatment.

Subjects who achieve a PASI50 response at Week 16 will continue therapy as follows:

- Subjects initially randomized to CZP 400mg Q2W will continue to receive CZP 400mg Q2W.
- Subjects initially randomized to CZP 200mg Q2W will be re-randomized (1:1) to receive either CZP 200mg Q2W or CZP 400mg Q4W (with PBO administered on alternate dosing weeks to maintain the blind).
- Subjects initially randomized to PBO will be continue to receive PBO.
- Subjects who do not achieve a PASI50 response at Week 16, 24, 32, or 40 will escape from double-blind treatment and receive open-label CZP treatment (400mg Q2W as 3 loading doses followed by CZP 200mg Q2W) from the visit the response criterion is not met. Subjects receiving open-label CZP 200mg Q2W in the escape arm and not achieving a PASI50 response will be allowed to have their dose increased to CZP 400mg Q2W at the visit the criterion is not met, at the discretion of the Investigator. If, in the opinion of the Investigator, the subject is not receiving benefit (eg, a PASI50) at the 400mg Q2W dose, the subject should be withdrawn from the study.

Subjects who do not achieve a PASI50 response at Week 16 will escape from double-blind treatment and receive treatment as follows:

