3.5.10 Escape Maintenance Set

The Escape Maintenance (EM) Set is only applicable for the final analysis. Analysis sets EM SS, EM FAS, EM PsAS and EM NAPSI are introduced for the final analysis, where the EM Set will consist of all subjects in the respective analysis set (SS, FAS, PsAs and NAPSI) who do not discontinue treatment during Initial Period and who have received at least 1 dose of escape study medication during the Maintenance Period. Analyses based on EM sets will include only data observed during escape treatment.

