4.2 Handling of dropouts or missing data

PASI 75/50/90/100 and PGA:

- Initial Period

Missing data for the primary variable and other key efficacy variables (eg, PASI50, PASI90, PASI100, and PGA) will be handled using the Markov Chain Monte Carlo (MCMC) method for multiple imputation. Sensitivity analyses which apply different methods of handling missing data for the primary endpoint are planned. Further details are provided in Section 8.1.3.

- Maintenance Period

Subjects can switch to the CZP 200mg Escape Arm (400mg Q2W as 3 loading doses followed by CZP 200mg Q2W) due to lack of PASI50 response at multiple time points (at Week 16 or later). They are treated as non-responders from the time of escape onwards for by

blinded maintenance group tables. Observed PASI50 responses after escape are only relevant for Escape Arm outputs. Other missing data will be handled using the MCMC method for multiple imputation.

Missing data after escape because of discontinuation after escape will be imputed accordingly.

For the cohort missing data will be imputed accordingly, and summaries will be based on MCMC imputed data and on observed case data over time.

Other Binary Efficacy Variables:

- Initial Period

Other binary efficacy variables that are summarized without statistical modeling will use non-response imputation (NRI) as the method for handling missing data. Non-responder imputation (NRI) is a method for dichotomous (“yes (1) or no (0)”) or categorical variables, where a subject is considered a non-responder if certain criteria are met. Typically, if a subject drops out of a study, that subject is analyzed as a non-responder, regardless of whether or not the subject was responding to treatment at the time of dropout.

- Maintenance Period

Other binary efficacy variables that are summarized without statistical modeling will use NRI as the method for handling missing data. Escapers will be treated as non-responders from the time of escape onwards for by blinded maintenance group tables. Observed data after escape is only relevant for Escape Arm outputs.

Missing data after escape because of discontinuation after escape will be imputed accordingly.

For the cohort missing data will be imputed, and summaries will be based on NRI imputed data and on observed case data over time.

Continuous Variables:

- Initial Period

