Escape Arm in Maintenance Period (Final Analysis, including data after escape for subjects who escaped at/after Week 16)

Observed PASI50, PASI75, PASI90 and PASI100 responder rates will be summarized by the treatment group before escape from Week 16 to Week 52 based on EM FAS. Observed results in maintenance period but before escape will not be included in this table.

Additionally, the observed PASI50, PASI75, PASI90 and PASI100 responder rates will be summarized by the treatment group before escape and by escape maintenance treatment group from Week 16 to Week 52 based on EM FAS. Due to up-titration, subjects may be presented in both escape maintenance treatment groups (Esc CZP 200mg Q2W, Esc CZP 400mg Q2W), so that the sum of the sample sizes of both treatment groups will exceed the number of escapers.

Combined Initial and Maintenance Period (Interim Analysis, excluding subjects who escaped at Week 16)

PASI50, PASI75, PASI90 and PASI100 responder rates will be summarized by randomized treatment group at each visit from Week 0 to Week 24 based on NRI and observed case data. Responder rates based on NRI data, odds ratios with corresponding 95% CIs will be derived without modelling but only by calculating counts, percentages and CIs. No p-values will be presented. For the NRI summary, subjects will be imputed as non-responders at the point of escape or for those subjects who do not escape, from the point of premature withdrawal through Week 24. For observed data, no imputation will be performed and counts and percentages of responders will be presented.

Combined Initial and Maintenance Period (Final Analysis, including subjects who escaped at/after Week 16)

PASI50, PASI75, PASI90 and PASI100 responder rates will be summarized by randomized treatment group at each visit from Week 0 to Week 52 based on NRI and observed case data. Responder rates based on NRI data will be derived without modelling but only by calculating counts and percentages. No p-values will be presented. For the NRI summary, subjects will

be imputed as non-responders at the point of escape or for those subjects who do not escape, from the point of premature withdrawal through Week 52. For observed data, no imputation will be performed and counts and percentages of responders will be presented.

Additionally, the same table will be produced at each visit from Week 0 to Week 52 based on FAS by the following groups:

- PBO

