Escape Arm in Maintenance Period (Final Analysis, including data after escape for subjects who escaped at/after Week 16)

Observed PGA responder rates will be summarized by the treatment group before escape from Week 16 to Week 52 based on FAS. Observed results in maintenance period but before escape will not be included in this table.

Additionally, the observed PGA responder rates will be summarized by the treatment group before escape and by escape maintenance treatment group from Week 16 to Week 52 based on FAS. Due to up-titration, subjects may be presented in both escape maintenance treatment groups (Esc CZP 200mg Q2W, Esc CZP 400mg Q2W), so that the sum of the sample sizes of both treatment groups will exceed the number of escapers.

Combined Initial and Maintenance Period (Final Analysis, including subjects who escaped at/after Week 16)

PGA responder rates will be summarized by randomized treatment group at each visit from Week 0 to Week 52 based on NRI and observed case data. Responder rates based on NRI data will be derived without modelling but only by calculating counts and percentages. No p-values will be presented. For the NRI summary, subjects will be imputed as non-responders

at the point of escape or for those subjects who do not escape, from the point of premature withdrawal through Week 52. For observed data, no imputation will be performed and counts and percentages of responders will be presented.

Additionally, the same table will be produced at each visit from Week 0 to Week 52 based on FAS by the groups described in detail in the PASI Section 8.3.1. Data will be summarized based on observed and NRI data.

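### Escape-arm PASI and PGA responder tables use observed data by study week, so withdrawal of subjects judged not to benefit biases the rates upward, and the SAP's imputation rules for these subjects conflict

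*SAP*

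**What the plan says.** - **SAP 8.3.1, Escape Arm in Maintenance Period (final analysis).** Observed PASI50/75/90/100 "responder rates will be summarized by the treatment group before escape from Week 16 to Week 52 based on EM FAS". A second table adds a split by escape dose, with the remark "Due to up-titration, subjects may be presented in both escape maintenance treatment" groups.
- **SAP 8.3.2, same heading.** "Observed PGA responder rates will be summarized by the treatment group before escape from Week 16 to Week 52 based on FAS". The layout matches PASI, but the set is FAS rather than EM FAS.
- **SAP 3.5.10.** "Analyses based on EM sets will include only data observed during escape treatment".
- **SAP 4.2, PASI and PGA, Maintenance Period.** "Missing data after escape because of discontinuation after escape will be imputed accordingly". No method is named; the nearest preceding sentence on missing data concerns MCMC. The same text confines the treatment of escapers as non-responders to tables by blinded maintenance group, and says post-escape responses serve the Escape Arm outputs. The opening of 8.3 applies 4.2 unless a subsection notes an exception.
- **SAP 8.3.1, Combined Initial and Maintenance Period (final analysis).** For the NRI summary, subjects will "be imputed as non-responders at the point of escape or for those subjects who do not escape", from premature withdrawal. A further version of this table has 'Esc' rows, on observed and NRI data. SAP 8.3.2 repeats it for PGA.
- **Protocol 5.1.1.3.** Subjects without PASI50 at Week 16, 24, 32 or 40 escape to open-label CZP. On 200mg Q2W, failure to reach PASI50 allows an increase to 400mg Q2W at the investigator's discretion. If, in the investigator's opinion, "the subject is not receiving benefit (eg, a PASI50) at the 400mg Q2W dose, the subject should be withdrawn from the study".

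**The concern.** Withdrawal in the escape arm is tied to the outcome being tabulated. A subject withdrawn for lack of benefit leaves the observed-case denominator at later visits, while responders stay.

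The escape treatment population is a named efficacy population (Protocol 4.1.3.1.4). Protocol 14.3 and SAP 8 expect most placebo subjects to switch to CZP, so these tables are where most of that arm's response to CZP will be seen. As written, the plan offers an observed rate selected upward and an NRI 'Esc' row that is literally zero after escape. Neither gives the share of escapers who respond.

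The study-week axis adds a second difficulty. Subjects escape at four different visits, so a change between weeks combines response to treatment, attrition and new entrants.

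**Working it through.** **Figures in the plan.** The documents state no escape-arm rate, number of escapers or withdrawal share, so there is no planned figure to reproduce. What follows is an illustration.

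**Inputs.** Assumed: 20 escapers; PASI50 80% (range 75-90%); PASI90 40%; share w of PASI50 non-responders withdrawn of 25%, 50% or 100%. PASI75 70% is borrowed from the Week 16 assumption for CZP 200mg Q2W in Protocol 14.8.1. That section's 15% placebo PASI75 rate implies a PASI50 rate of at least 15%, so at most 25 × 0.85 = 21.25 placebo subjects would be expected to escape at Week 16.

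**Effect of withdrawal (table by treatment before escape).** Let p be the response rate among all escapers and p50 their PASI50 rate. If a share w of PASI50 non-responders has left:

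observed rate = p / (1 − w(1 − p50)); NRI rate = p.

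With p50 = 80% the denominators are 0.95, 0.90 and 0.80:

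| Endpoint | NRI | w = 25% | w = 50% | w = 100% |
|---|---|---|---|---|
| PASI50 | 80% | 84% | 89% | 100% |
| PASI75 | 70% | 74% | 78% | 87.5% |
| PASI90 | 40% | 42% | 44% | 50% |

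At w = 50%, PASI50 of 75% shows as 0.75/0.875 = 86%, and 90% as 0.90/0.95 = 95%. At w = 100%, PASI75 of 70% shows as 93% if p50 is 75% (0.70/0.75) and 78% if p50 is 90% (0.70/0.90).

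**Effect of dose increase (table split by escape dose).** Of 20 escapers, 16 reach PASI50. If the other 4 all move to 400mg, and each column holds visits on that dose, Esc 200mg shows 16/16 = 100% and Esc 400mg starts at 0/4. In the table by treatment before escape the rate stays 16/20 = 80%, because a dose increase removes nobody.

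**Effect of later escapers.** They enter having just failed PASI50. Adding 2, 4 or 6 who have not yet responded to 16/16 gives 16/18 = 89%, 16/20 = 80% and 16/22 = 73%. This changes the shape over study weeks. It does not change the ordering at a given week: both methods count the same responders, and NRI adds the withdrawn subjects to the denominator, so the observed rate cannot be below the NRI rate.

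**Time on escape treatment.** At Week 44, a Week 16 escaper has had 44 − 16 = 28 weeks and a Week 40 escaper 44 − 40 = 4 weeks. By Week 52, escapers at Weeks 16, 24, 32 and 40 reach 36, 28, 20 and 12 weeks.

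**Imputation texts side by side.** If 'Observed' in 8.3.1 and 8.3.2 is an exception to 4.2, the tables carry the bias above. If 4.2 governs, an imputation is due but its method is not stated. The combined table's NRI rule, taken literally, sets every 'Esc' row to non-response after escape, which conflicts with the limit in 4.2 to blinded maintenance group tables.

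**The case against.** The strongest reply is that these are open-label, descriptive summaries of other efficacy variables, without p-values and confined to the final analysis. Attrition will be visible: SAP 8.3.1 acknowledges that the observed sample size in the 'Esc' rows moves with later escapes and withdrawals, and 5.1 plans disposition by escape group. Observed-case summaries by escape group are also used for PASI score, PGA distribution, BSA and DLQI response (8.3.3, 8.3.4, 8.3.6, 8.3.7), so the NRI version for ACR in 8.3.9 does not show that PASI and PGA are anomalous. All of this stands and limits the importance of the point.

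A reader might infer four stronger things that the documents do not support:

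- **That the rates climb to 100%.** That is a limiting case for PASI50, if every PASI50 non-responder is withdrawn. PASI75, PASI90, PASI100 and PGA reach 100% only if every remaining subject meets the stricter criterion.
- **That both escape-dose columns lose non-responders by rule.** Dose increase is discretionary and sends non-responders into the 400mg column, lowering it at first. Withdrawal rests on investigator opinion, with PASI50 only as an example.
- **That withdrawn subjects vanish at once.** SAP 3.2.4 maps the early-withdrawal assessment to the next scheduled visit, so it still counts once. The bias is delayed, not removed.
- **That no imputation is planned.** SAP 4.2 mentions it and the 'Esc' rows have an NRI version. The defect is that the texts conflict and yield no usable rate.

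**Conclusion.** The point stands as an upward bias in the stand-alone escape-arm PASI and PGA tables, together with an unresolved conflict between SAP 4.2 and 8.3.1/8.3.2. The direction follows from the text wherever withdrawal is for lack of benefit. The size depends on how many non-responders are withdrawn, which the documents do not give. In the illustration it is 4 to 9 percentage points for PASI50 and 4 to 8 for PASI75 at withdrawal shares of 25-50%.

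In the table split by escape dose, up-titration separately raises the Esc 200mg column and initially lowers the Esc 400mg column. Whether the plotted rates rise or fall over study weeks cannot be predicted, because later escapers pull them down.

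The primary and alpha-controlled Week 16 analyses are untouched. The change is still worth making, because as planned no table gives a usable response rate for all subjects who escaped.

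**What to change.** 1. Reconcile SAP 4.2 with 8.3.1 and 8.3.2, and name the method for discontinuation after escape. Add an NRI version of the escape PASI and PGA tables on EM FAS by treatment before escape, keeping subjects who withdraw after escape in the denominator as non-responders. Keep observed case alongside.
2. State that the rule making subjects non-responders from the point of escape does not apply to the 'Esc' rows of the combined Week 0-52 table. There, only withdrawal after escape is imputed as non-response.
3. Add a supportive display by weeks since escape. Limit the denominator at each time to subjects whose escape visit allows that follow-up by Week 52 (36, 28, 20 and 12 weeks for escapes at Weeks 16, 24, 32 and 40). A fixed denominator out to 36 weeks would count later escapers as non-responders at times they cannot reach.
4. Use EM FAS for PGA as for PASI.

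Counting a dose increase as non-response in the Esc 200mg column is optional. None of this alters the clinical rules for dose increase or withdrawal. The cost is SAP wording and a little more programming, with no new data; the escape-arm rates will look less favourable.

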8.3.3 PASI score (absolute)

See Section 8.1 for details of the derivation.

Initial Period

The absolute PASI score and the (percentage) change from Baseline will be summarized by randomized treatment group at each time point through Week 16 for the FAS using descriptive statistics for continuous data. Missing data will be imputed using LOCF.

Observed case data (without LOCF) in the Initial Period will be presented using descriptive statistics for continuous data by visit and by randomized treatment group for FAS and EPS.

Line plots will be generated to present mean percent change from Baseline in PASI score by randomized treatment group through Week 16.

Maintenance Period

Results will be summarized by visit and blinded maintenance treatment group for the FAS using descriptive statistics for continuous data. LOCF will be used to impute all missing data.

Subjects who switch to the escape arm will have their data at the escape time point carried forward until the end of the treatment period.

Observed case data (without LOCF) in the Maintenance Period will be presented using descriptive statistics for continuous data by visit and by blinded maintenance treatment group or escape maintenance treatment group for the FAS and by maintenance treatment group for the EPS.

Line plots will be generated to present mean percent change from Baseline in PASI score by randomized treatment group (Initial Period treatment) over time (from Week 0 to Week 24/Week 52).

8.3.4 PGA score distribution

See Section 8.2.1 for details of the derivation. The summaries described in this section are based on observed data – no imputation will be performed.

Initial Period

The distribution of the PGA score (0, 1, 2, 3, or 4) will be summarized in shift tables comparing the change from Baseline versus post-Baseline (Weeks 2, 4, 8, 12 and 16) by randomized treatment group for the FAS and EPS. The shift tables will be provided for each time point.

Maintenance Period

The distribution of the PGA Score will be summarized in shift tables comparing the change from Baseline versus post-Baseline (Weeks 16, 20, 24, 28, 32, 36, 40, 44, 48 and 52) by blinded maintenance or escape maintenance treatment group for the FAS and by maintenance treatment group for EPS. The shift tables will be provided for each time point.

8.3.5 Time to PASI50, Time to PASI75, Time to PASI90, Time to PASI100

See Section 8.1.1 for details of the derivation of PASI50, PASI75, PASI90 and PASI100 response.

Initial Period

Time to PASI50, PASI75, PASI90 and PASI100 response will be evaluated using Kaplan-Meier methods for the time in days to achieving the response, comparing each CZP dose to placebo. Time to PASI50, PASI75, PASI90 and PASI100 response will be defined as the time interval in days from Baseline until the first date when the given response is achieved. Subjects who discontinue prior to achieving a response will be censored at the date of study drug discontinuation. Subjects who reach the Week 16 visit without achieving a response will be censored at date of the Week 16 visit.

Between groups differences (ie, each CZP dose vs placebo) will be analyzed with the log-rank statistics. Median time to response will be presented for each randomized treatment group. Kaplan-Meier plots of the time to PASI50, PASI75, PASI90 and PASI100 response by treatment group will be provided.

8.3.6 BSA affected by PSO (absolute, percent change)

The BSA palm method will be used for the evaluation of BSA as follows:

Body surface area estimation uses the palm (subject's flat hand and thumb together, fingers included) as representing around 1% of the total BSA.

- Subject's palm = 1%
- Head and neck = 10% (10 palms)
- Upper extremities = 20 % (20 palms)
- Trunk = 30% (30 palms)
- Lower extremities = 40 % (40 palms)
- Total BSA = 100%

The investigator will evaluate the percentage involvement of psoriasis on each subject's BSA on a continuous scale from 0% (no involvement) to 100% (full involvement) at Baseline, Week 16 and Week 52. BSA data will be summarized as observed – no imputation will be performed.

Initial Period

At Week 16 the absolute score, change from Baseline score (Week 16 – Baseline) and percentage change from Baseline score (change from Baseline at Week 16/Baseline) will be summarized by randomized treatment group based on the FAS and EPS using descriptive statistics for continuous data.

Maintenance Period

The absolute score, change from Baseline score (Post-Baseline – Baseline) and percentage change from Baseline score (change from Baseline/Baseline) will be summarized by visit (Week 16 and Week 52) and blinded or escape maintenance treatment group based on the FAS and also by maintenance treatment group based on EPS using descriptive statistics for continuous data.

8.3.7 Change from Baseline in DLQI, percent of subjects achieving MCID, and percent achieving DLQI remission

At each post Baseline visit, the change from Baseline in DLQI, percent of subjects achieving minimal clinically important difference (MCID), and percent of subjects achieving DLQI remission, will be reported. See [Section 8.2.3](#) for the derivation of the change from Baseline in DLQI score.

Change from Baseline in DLQI

The approach for summarizing the actual scores and change from Baseline scores over time in DLQI for the Initial Period and the Maintenance Period on observed and LOCF imputed cases will follow the same approach used for summarizing PASI scores as described in [Section 0](#). Percent change from Baseline will not be summarized, but results based on LOCF on CFAS will be provided. Note that the change from Baseline in DLQI at Week 16 is also a key secondary efficacy variable and will be subject to statistical testing as described in [Section 4.5](#).

Treatment group comparisons for each CZP treatment group vs placebo will be performed using an analysis of covariance (ANCOVA) model with treatment group and prior biologic exposure as factors and Baseline DLQI score as a covariate. The least squares (LS) means and standard errors derived from the model will be presented for each treatment group. Additionally, adjusted mean treatment differences, corresponding confidence intervals, and p-values will be reported. Missing values will be imputed using LOCF.

A line plot will be generated to present adjusted mean change from Baseline in DLQI by randomized treatment group through Week 16.

Percent of subjects achieving MCID or DLQI remission

At a given visit, a subject will be considered to have achieved MCID if their individual improvement from Baseline score is ≥ 4 . A 4-point improvement in the DLQI score (DLQI response) has been reported to be meaningful for the subject.

At a given visit, a subject will be considered to have achieved remission if their absolute DLQI score is ≤ 1 .

Initial Period

DLQI MCID responder rates and subjects with DLQI remission will be summarized by visit and randomized treatment group for the FAS and CFAS. Missing data will be imputed using NRI. A summary of corresponding results based on observed cases will be provided by visit and randomized treatment group for the FAS and CFAS.

A comparison between treatment groups vs Placebo will be made at each time point using logistic regression models based on NRI imputed data and observed data. The estimate for the responder rate, the odds ratio, 95% CI, and p-value from the model will be presented.

Maintenance Period

For the maintenance phase, MCID responder rates and subjects with DLQI remission will be summarized by visit and blinded maintenance treatment group for the FAS and CFAS. Missing data will be imputed using NRI. Additionally, a summary of corresponding results based on observed cases will be provided by visit and (blinded) maintenance treatment group for the FAS and CFAS, and by escape maintenance treatment group for the FAS.

8.3.8 Change from Baseline in Itch Numeric Rating Scale, percent of subjects achieving MCID or remission

At each post Baseline visit, the change from Baseline in Itch Numeric Rating Scale and percent of subjects achieving minimal clinically important difference (MCID) or remission, will be reported. See [Section 8.2.4](#) for the derivation of the change from Baseline in Itch Numeric Rating Scale.

Change from Baseline in Itch Numeric Rating Scale

The approach for summarizing the actual and change from Baseline scores over time in Itch Numeric Rating Scale for the Initial Period and the Maintenance Period on observed and LOCF imputed cases will follow the same approach as used for summarizing PASI scores, described in [Section 0](#). Percent change from Baseline will not be summarized, but results based on LOCF on CFAS will be provided. A line plot will be generated to present change from Baseline in itch severity by randomized treatment group through Week 16.

Percent of subjects achieving MCID, or remission

At a given visit, a subject will be considered to have achieved MCID if their individual improvement from Baseline score is ≥ 4 . A 4-point improvement in the Itch Numeric Rating Scale has been reported to be meaningful for the subject.

At a given visit, a subject's remission is defined as reaching an Itch Numeric Rating Scale of zero.

The summary of the results for subjects achieving MCID or Itch Numeric Rating Scale remission will be done analogous to analysis described in [Section 8.3.7](#).

8.3.9 ACR20, 50, 70 response criteria and change from Baseline in all individual ACR core components

For subjects with psoriatic arthritis (PsA), the American College of Rheumatology 20%/50%/70% response criteria (ACR20, ACR50, and ACR70) will be evaluated. The analysis will be based on the PsA Set and on the PsA Set including only subjects with 3 or more tender joints and 3 or more swollen joints at Baseline.

A subject will be considered an ACR20/50/70 responder if:

The counts for both tender joint count (TJC) and swollen joint count (SJC) (68/66 joint counts) ([Section 8.3.10](#)) have reduced by 20/50/70% or more, respectively, from the Baseline assessment

and

There is a 20%, 50%, 70% or greater improvement in at least 3 of the 5 remaining core set measures:

- Physician's Global Assessments of Disease Activity (PhGADA, [Section 8.3.11](#))
- Patient's Global Assessments of Disease Activity (PGADA, [Section 8.3.12](#)),
- Patient's Assessment of Arthritis Pain (PAP, [Section 8.3.13](#)),
- Health Assessment Questionnaire Disability Index (HAQ-DI, [Section 8.3.14](#)),
- C-reactive protein (CRP).

If any of these assessments have missing values, the ACR20/50/70 response will be determined on the basis of the non-missing values as stated above. If that is not possible, the

ACR response will be set to missing. Missing items for the components TJC, SJC, and HAQ-DI will be handled as described in [Section 8.3.10](#) and [Section 8.3.14](#).

The number of subjects with a ACR20/ACR50/ACR70 response will be tabulated by randomized treatment group and visit for the Initial Period and by blinded maintenance treatment group or escape maintenance treatment group for the Maintenance Period, based on observed data and NRI imputed data. The treatment differences: CZP 200mg Q2W – PBO and CZP 400mg Q2W - PBO and All CZP – PBO (and corresponding 95% CI and p-value) are estimated at every visit during Initial Period, using a standard two-sided Wald asymptotic test with a 5% alpha level. The corresponding 95% CI for the differences are constructed using their asymptotic standard errors (asymptotic Wald confidence limits).

Line plots will be generated to present the percentages of responders over time by randomized treatment group for the Initial Period and by blinded maintenance treatment for the Maintenance Period based on NRI imputed data.

Tables for the absolute values and changes vs. Baseline will be provided for each of the core measures (swollen joint count, tender joint count, PhGADA, PGADA, PGAAP, HAQ-DI, CRP, mNAPSI and DAS28(CRP)) by treatment group and visit for the Initial and Maintenance Period based on Observed case and LOCF imputed data. The treatment differences vs. PBO (LSMeans, 95% CI, p-value) are estimated at every visit during Initial Period, using a ANCOVA model with treatment and prior biological exposure (yes, no) as factors and Baseline score as covariate.

Same tables will be provided for the Escape Arm.

